1. Proton Pump Inhibitor Cohort (PPI)

The PPI cohort will be defined as patients with prescriptions for any PPI at any dose for 90 consecutive days in patients of any age.

2. Diabetes – Hypoglycemia Risk (DM-HR)

To create diabetes cohorts, we identify overly-controlled patients with diabetes based upon International Classification of Diseases, Tenth Revision, Clinical Modification (ICD-10-CM) diagnosis codes, most recent HbA1c <7%, as well as one or more of the following criteria: 1) age 65 or older, 2) renal insufficiency defined as creatinine >2 mg/dL, or 3) cognitive impairment defined by a diagnosis of cognitive impairment and/or prescription for an acetylcholinesterase inhibitor (e.g., donepezil). Patients in the DM-HR group needed to have a current prescription for either insulin or sulfonylurea with at least 90 consecutive days on the medication in the prior year.

3. Gabapentin (Gaba)

The gabapentin cohort will include patients prescribed a total daily dose of gabapentin >1800mg for a minimum of 90 days.

Subject Exclusion Criteria

We will not exclude women or minorities, but children will not be eligible for participation.

1. Proton Pump Inhibitor Cohort (PPI)

In response to feedback from our pilot study, we will exclude diagnoses for which PPI continuation would be appropriate (e.g., Barrett’s esophagus, or those prescribed chronic glucocorticoids or NSAIDs).

2. Diabetes – Hypoglycemia Risk (DM-HR)

No exclusion criteria.

3. Gabapentin Cohort (Gaba)

We will exclude patients with recommended indications for gabapentin, including documented neuropathic pain using established criteria, those with seizure disorders, documented neuropathic pain, and cancer-related pain.

Recruitment

As we did for our IRB approved pilot study, we are requesting a waiver of informed consent and a waiver of HIPAA authorization to identify eligible Veterans to whom we will mail brochures.

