Note about Patients with Cognitive Impairment – Due to the eligibility criteria for the Diabetes cohort, it is possible that patients with cognitive impairment will be recruited. Veterans with cognitive impairment represent a population at potentially increased risk for worsened outcomes associated with overtreatment of diabetes, especially for hypoglycemia (low blood sugar). Thus, it is important to understand the effect of promoting deprescribing on this vulnerable population. Veterans with mild cognitive impairment may still comprehend the brochure well enough to ask their primary care provider about the need for diabetes medication. Veterans with more severe cognitive impairment may not interact with the brochure, but a caregiver may on their behalf. Veterans with cognitive impairment significant enough to not interact with the brochure are likely at *greater* risk of harm from potentially inappropriate medication use and subsequent risk for hypoglycemia than they are from hyperglycemia should they decide to stop taking their medication prior to discussing with their PCP.

Data Collection/ Study Measures

Data collection procedures

Before starting the trial and mailing medication-specific brochures, using material similar to that in our pilot study, we will inform clinicians (attending physicians, nurse practitioners, physician assistants, and clinical pharmacy specialists) and staff via either Outlook or Enterprise Feedback Management (Verint)-managed email about the project, describe an overview of deprescribing, and provide them with deprescribing algorithms and guidelines available online. The intention is to prepare providers to respond to a patient engaged by the medication-specific brochure, as the patient is the focus of the proposed intervention. When the patient cohort changes, prescribers will receive “refresher” emails, for a total of three points of contact during the intervention.

Chart review – We will conduct chart reviews on a sample of subjects; this activity will assess the concordance of the medication dispensing data obtained from CDW with that of both electronic health record documentation.

Study Measures

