We will query CDW for 6 months following the date of each scheduled primary care visit to assess our primary outcome of deprescribing. Based upon findings in our pilot study, medication orders may not be discontinued in electronic health records even if discussions occur in the clinic visit (e.g., the PCP tells the patient to deprescribe but does not change the order). Notably, because our primary objective is to improve safe prescribing and reduce PIMs, pharmacy dispensing data best reflects our deprescribing outcome. As per our definition, either complete cessation or dose reduction will be fulfillment of our primary outcome.

Modeling our approach after the methods of Steinman, Sussman, and Martin, we will use non-refill of the medication in the 6 months following the primary care appointment as our a priori definition of cessation, based upon dispensing dates.^{4,5} Per VA Pharmacy policy, medications are only refilled upon request, and therefore, non-refill of a medication can indicate that it was discontinued, it expired (typically one year after it was ordered), or the patient did not refill it. If the medication continues to be dispensed, we will determine any reduction in the total daily dose, indicating de-escalation (one component of our deprescribing definition). An

exception to the de-escalation rule will be for insulin, where only complete cessation will qualify since dose changes are less likely to be reflected in the order compared to oral medications.

Consistent with our conceptual framework, we will also assess patient and provider factors that may influence deprescribing. Patient factors will be obtained from CDW, and will include age, race, sex, Elixhauser comorbidities in the two years prior to the scheduled primary care visit. Provider factors include sex, discipline, age, and site.

To assess potential ADWEs, we will ascertain if the deprescribed medication is subsequently restarted or returns to original dosing. We will then query CDW for diagnoses of GI bleeding for the PPI cohort, diabetic ketoacidosis or hyperosmolar hyperglycemic state for the DM cohort, and seizure for the gabapentin cohort in the year following the index visit. Note, we consider substitution to a lower potency medication (e.g., histamine-2 receptor antagonist for a PPI) to be a neutral or desirable event and not an ADWE.

Statistical Analysis Plan (see attached statistical analysis plan for greater detail)

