Official Title: Engaging Patients to Promote Deprescribing

NCT Number: NCT04294901

Document Date: November 14, 2019

Statistical Power

Based on fiscal year (FY) 2017 data, we estimated that we would mail brochures to at least 1,990 PPI patients, 894 Diabetes-Hypoglycemia patients, and 758 Gabapentin patients during the study. For apriori statistical power analyses, we made the following assumptions based on our pilot data: an overall baseline deprescribing rate of 4.21%, a conservatively high intraclass correlation coefficient (ICC) of 0.05 (for non-independence among patients of the same provider), an average of 20 eligible patients per PCC or WHC provider, and a 20% attrition rate (i.e., patients who receive the intervention brochure but do not attend their clinic visit). With these assumptions, we determined that we would have 80% power (for two-tailed tests at $\alpha=0.05$) to detect deprescribing rates following the intervention as small as 6.55% overall for these low-end estimates of our projected sample. Moreover, even at these low-end estimates of the projected sample size, we determined we would have 80% power to detect an overall deprescribing rate as low as 15% among the combined intervention cohorts even if the ICC was as high as 0.1, the baseline deprescribing rate was as high as 10%, and/or the attrition rate was as high as 40%. Notably, a deprescribing rate of 15% was reasonable to expect given that we found similar or higher rates in our pilot study.

We conducted analyses using SAS.³

Endpoints & Covariates

The primary hypothesis was deprescribing would be greater for Veterans receiving the intervention brochure than for those in the historical control group.

The primary outcome was binary: deprescribing versus not, assessed via pharmacy dispensing data from the VA Corporate Data Warehouse (CDW). More specifically, six months from the index date, an analyst queried the CDW to determine medication outcomes (e.g., complete deprescribing, dose reduction). We selected 6 months because prescriptions are often filled as a 90-day supply and using a shorter observation window might not fully identify that the prescription was not refilled. We removed patients who died within six months from their index data from intervention and historical controls at the analysis stage to avoid misattributing deprescribing to the intervention rather than death.

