To identify dose reductions, we calculated the total daily dose (TDD) of the target medication as [dose*(quantity/days supplied)].^{1,2} Substitutions within a medication drug class (e.g., pantoprazole to omeprazole) were standardized to one medication within each class. We only compared TDD at 6 months to that at the index visit for oral medications because insulin dose adjustments are not consistently documented within the electronic health record. Combination insulin products were separated into their long acting and short acting components and analyzed separately. We allowed a 10% buffer for days' supply of PPI, sulfonylurea, and gabapentin (e.g., 33 days for a 30-day supply) to account for missed doses and 100% buffer for insulin due to dispensing requirements (e.g., minimum vials dispensed regardless of dose).

Patient factors and provider characteristics (age, gender, profession) were included as covariates in the model. Based on our conceptual model and using data from CDW, patient factors included age, race, sex, and Elixhauser comorbidities in the year prior to the scheduled primary care visit.^{4,5}

Additionally, we planned to examine whether the effectiveness of the brochure intervention was associated with target medication.

Interim & Final Analysis

Our primary comparisons were between “brochure-intervention” patients and “historical control” patients (matched in terms of eligibility) from the same primary care provider. To investigate the impact of the intervention brochure on deprescribing, Hierarchical Generalized Linear Modeling (HGLM) was used to account for the nesting of patients within providers. This approach provided information not just about the average effectiveness of the intervention, but also about how much variation there is in the intervention impact across providers. In all models, Level 1 (patient-level) intercepts and slopes were treated as random effects, and parameters were estimated with robust standard errors. Using this approach of nesting patients within providers at intervention sites, for our primary analysis, we compared the likelihood of deprescribing among patients in the pre-intervention (“historical”) period to that for patients in the intervention periods who were mailed the brochure. We predicted that intervention patients would be significantly more likely to have deprescribing than patients in the pre-intervention period with the same eligibility criteria. We then examined whether the

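### Does the primary outcome lack a coding rule for a patient whose last oral fill after the visit has run out by month 6?

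*Protocol*

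**What the plan says.** **Protocol, Study Measures.** Cessation: "we will use non-refill of the medication in the 6 months following the primary care appointment as our a priori definition of cessation", based on dispensing dates. Dose step: "If the medication continues to be dispensed, we will determine any reduction in the total daily dose". For insulin, only complete cessation counts.

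**SAP, Endpoints & Covariates.** The data warehouse is queried six months from the index date. The window was set at 6 months because 90-day supplies are common and "using a shorter observation window might not fully identify that the prescription was not refilled". TDD is computed from a fill, as dose times quantity over days supplied, and "We only compared TDD at 6 months to that at the index visit for oral medications". A 10% allowance on days' supply is made for PPI, sulfonylurea and "gabapentin (e.g., 33 days for a 30-day supply) to account for missed doses". Insulin gets 100%, because vials come in minimum quantities.

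**Protocol, Medication Groups.** All three cohorts require a 90-day run of supply. For the diabetes cohort this is "at least 90 consecutive days on the medication in the prior year".

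**Protocol, Data collection procedures.** A chart review on a sample will "assess the concordance of the medication dispensing data obtained from CDW" against the health record.

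**The concern.** The primary outcome is built from dispensing records, so every pattern of fills needs a code. Take a 90-day oral fill on day 20 at the index dose, with nothing later. The patient did refill, so the Protocol's cessation test is not met. Two months before month 6 the supply is gone, so it is unclear whether the drug still counts as being dispensed, and no fill is current from which to read a TDD at 6 months. TDD could be set to zero (event), taken from the last fill (non-event) or left missing.

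The buffers add to the doubt. A test that asks only whether any fill occurred in six months has no use for a days'-supply allowance. If the buffers served the outcome, cessation was judged on coverage and not on refill, which would depart from the definition that the Protocol calls a priori. With a planning baseline of only 4.21%, even a small group moved from non-event to event would change the reported rates.

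**Working it through.** **1. Which fill patterns are open?** Let f be the day of the last fill after the visit, D its days' supply, b the buffer, and month 6 day 182. The fill has lapsed if f + D(1+b) < 182. Compare the literal Protocol rule with a coverage rule (no current supply at month 6 is an event):

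| Pattern | Literal rule | Coverage rule |
|---|---|---|
| No fill after the visit (supplies of up to 90 days) | event | event |
| Oral, last fill current at month 6 | compare TDD | compare TDD |
| Oral, last fill lapsed, dose lower than index | event | event |
| Oral, last fill lapsed, dose unchanged | non-event | event |
| Insulin, any fill after the visit | non-event | event only if lapsed with the 100% buffer |

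Only the fourth row is materially open. For insulin in 90-day fills, 90 × 2 = 180 days of cover, so a fill lapses by day 182 only if made by about day 182 − 180 = 2.

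**2. Where the cut falls for 90-day oral fills.** Without the buffer: 182 − 90 = day 92. With 10%: 182 − 99 = day 83. The buffer moves the cut by 9 days. The day-20 example runs out on day 20 + 90 = 110, or 20 + 99 = 119 with the buffer, which is 72 or 63 days before day 182. So the size of the oral buffer matters little. What matters is whether days' supply enters the outcome at all.

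**3. How many stops could fall there?** The documents give no refill or stop timing, so this is illustration only. Assume on-time refills, the next one due on day R, uniform on (0, L), and the stop on day S, uniform on (0, W). A stop falls in the open group if R < S.

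- For W ≤ L the share is W/(2L). With L = 90: 30/180 = 17%, 60/180 = 33%, 90/180 = 50% for W = 30, 60, 90. If all stop at the visit, 0%.
- For W ≥ L the share is 1 − L/(2W). With L = 30: 50%, 75%, 83% for W = 30, 60, 90. The last two include patients with several fills after the visit. Exactly one fill has probability L/W: 30/60 = 50% and 30/90 = 33%.

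The SAP says that 90-day fills are common; 30 days appears only in its buffer example. The brochure is mailed two weeks before the visit to prompt a discussion there, which favours the low end. The denominator is true stops, not patients, so these shares are not event rates.

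**4. What would move in the comparison?** First, the plan's own figure. The projected sample is 1,990 + 894 + 758 = 3,642; after 20% attrition, 2,913.6. The design effect is 1 + 19 × 0.05 = 1.95, so the effective size is 1,494 per group with 1:1 controls (assumed). Power for 4.21% against 6.55% is 0.81, which matches the stated 80%.

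Now let a share q of each group be in the open row, unaffected by the brochure and not already in the 4.21%. Under the literal rule nothing moves. Under the coverage rule both rates rise by q and the difference stays at 6.55 − 4.21 = 2.34 points. At q = 1% the rates are 5.21% and 7.55%, and power is 0.75. At q = 5% they are 9.21% and 11.55%, and power is 0.56. Both values of q are assumptions.

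**5. Bias.** The same records, window and rule serve the brochure and historical groups. If the brochure does nothing, and refill habits are alike in the two periods, the open row is equally full in both groups under either reading, so the comparison stays fair.

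**The case for a change.** The strongest case for a change rests on insulin. Insulin doses are never compared, so its 100% buffer cannot serve the dose step. It must serve either cessation or a supply test such as eligibility, and the SAP says neither. The buffer sentence follows the TDD text under the endpoint heading, which points towards an outcome use. The SAP is dated November 2019 but cites 2024 software documentation and reports results, so its date does not show that the buffers were fixed before outcomes were known.

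What stands is that the step is not stated, and that the chart review, which checks data, does not supply it. What does not stand is that the outcome rule was therefore changed. All three cohorts, insulin included, need a 90-day run of supply to qualify, and an allowance for missed doses or vial sizes is a natural way to join fills into such a run. The SAP's reason for the 6-month window still speaks of non-refill. The TDD formula exists only for a fill, so it yields no zero when there is none; the last fill is the direct source. Both documents also cite the same two earlier studies for these methods. Those studies may settle the point, but they are not available here and nothing above relies on them. The SAP's date is a separate documentation matter and shows nothing about this rule.

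**Conclusion.** The gap is one of description. It is confined to oral drugs where the last fill after the visit is at the index dose and has lapsed by month 6. Even there, the Protocol's wording gives a usable default: a fill occurred and the dose did not change, so the patient is a non-event. An analyst following the text would code it so. The alternative, counting lapsed supply as a stop, is also defensible. Neither reading makes the comparison unfair, provided that one rule was run in both periods and refill habits did not shift between them.

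The number of patients involved cannot be derived from the documents. The 0% to 50% range for 90-day fills depends on assumed stop timing, and the power figures on an assumed group size. No wrong result from the plan as written has been shown, and no better method is at issue: all that could be asked is a statement of the rule already run. If that was the non-refill rule, nothing is affected. No change to the plan follows. Confidence is moderate, because the buffers' step remains unstated.

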remaining medication group at the start of the third (month 13) window. Our primary comparisons are between “brochure-intervention” patients and “baseline” patients (matched in terms of eligibility) from the same provider. Each patient will only have one opportunity to receive a brochure, even if they subsequently meet eligibility criteria for receipt of a second, different brochure. This allows equal exposure to the intervention for all Veterans since the impact of a second brochure might be influenced by the first brochure.

Although our primary comparison is between patients of the same provider pre- and post-intervention, we will also collect data at non-equivalent control sites matched by geography who will not receive the intervention; all data on control patients will be from the Corporate Data Warehouse (CDW). Including additional control sites will allow us to address potential temporal trends in deprescribing over the timeframe of our study that are not due to our intervention. The use of separate control sites (rather than randomizing some PCPs at each intervention site to control conditions) was preferred due to concerns about potential contamination across intervention and control conditions within sites. For both the control sites and the pre-intervention baseline period, we will identify patients who would have been eligible for the study; patients meeting criteria for multiple cohorts will be randomly allocated to only one.

Study Cohorts

The intervention cohort will consist of eligible patients in one of the three medication groups with an upcoming PCP appointment during the study enrollment period. We will create a comparison historical control cohorts comprising eligible patients in each medication group who were seen by the same PCPs at the same sites as our intervention cohort eighteen months to one year before our intervention cohort window to allow for comparable follow-up time before the intervention commenced. Patients in the intervention cohorts will be excluded from the historical control cohorts.

Medication Groups

To be enrolled in the study intervention or control cohort, patients needed to meet eligibility criteria for one of three medication-based groups. We have selected three medication-based patient groups based upon variations in 1) type of potentially inappropriate use, 2) medication factors (potential benefit and harms of continued use), and 3) anticipated interest in deprescribing by patients and providers.

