intervention effectiveness was moderated by the target medication. We did not expect a discontinuation rate of 100%, as patients may have an indication to remain on the medication. No adjustments were made to p-values or confidence intervals for multiple comparisons for the primary outcome.

No interim analyses were planned.

Missing Data

We examined the incidence of missing data by medication cohort (PPI vs. DM vs. Gaba). We expected very low rates of missing data, given that our primary analyses rely on CDW data. For missing data, we implemented a series of sensitivity analyses using imputation (coding as “missing” for categorical variables and imputed means for continuous variables) to assess the degree of bias that might be induced by missing data. The results did not change in direction or significance.

Methods for dealing with data transformations

We did not apply any data transformations. All data underwent standard preliminary visualization and quality screening to test for potential violations of assumptions (e.g., distributional assumptions regarding normality, homogeneity of variance, linear relationships, outliers, ceiling/floor effects).

Other analytical subsets

The intervention is designed to target and engage patients, but it is possible that the intervention may be more effective with certain providers. Therefore, a null hierarchical model was used to estimate intraclass correlations to characterize the percent variance explained at the patient, provider, and site levels.

We used HGLM to examine whether the likelihood of deprescribing changes over time at our control sites (instead of from the pre-intervention period) to rule out alternative explanations for the effect of our intervention that rely on temporal trends in deprescribing unrelated to our intervention (e.g., other deprescribing initiatives). We elected not to include temporal deprescribing trends in the manuscript since there was no evidence of significant temporal trends.

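### Leaving VA care is scored as deprescribing, and removing later brochure recipients from the historical controls would, other things equal, inflate the control rate by an amount the documents do not let us fix

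*Protocol*

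**What the plan says.** **Outcome.** The Protocol (Study Measures) takes "non-refill of the medication in the 6 months following the primary care appointment as our a priori definition of cessation". It lists what a missing refill may mean: the drug was discontinued, "it expired (typically one year after it was ordered), or the patient did not refill it". Leaving VA care is not named, and neither document requires any continuing VA activity before a non-refill is scored.

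**Exits that are handled.** The SAP (Endpoints & Covariates) says "We removed patients who died within six months from their index data from intervention and historical controls at the analysis stage", and gives the reason as "to avoid misattributing deprescribing to the intervention rather than death". The SAP (Missing Data) adds "We expected very low rates of missing data, given that our primary analyses rely on CDW data" and does not mention patients who go elsewhere. The Protocol (Data collection procedures) says "We will conduct chart reviews on a sample of subjects" to check concordance with the health record, without a rule for changing an outcome.

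**Controls.** The Protocol (Study Cohorts) draws them from patients seen by the same providers "eighteen months to one year before our intervention cohort window", and then states "Patients in the intervention cohorts will be excluded from the historical control cohorts".

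**Entry.** Controls were seen by the provider. Intervention patients enter on an upcoming appointment, and the SAP (Interim & Final Analysis) compares those who were mailed the brochure. The SAP (Statistical Power) assumes that 20% of those mailed do not attend.

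**The concern.** The SAP accepts that vanishing from dispensing data is not the same as deprescribing, but applies this to death alone. A patient who moves to non-VA care never shows as missing. That patient is an event.

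The control exclusion then makes the two groups unlike. A control indexed 12 to 18 months before the intervention window has a six-month outcome that closes 6 to 12 months before that window. Whether the person is later removed depends on what happens afterwards: still in VA care, on a qualifying drug, with an appointment in the right window. A control who stayed and continued can be removed. One who left cannot be, unless they return. One who stopped cannot be, unless they restart or qualify on another target drug. Intervention patients face no matching filter. The controls that remain are therefore enriched for events, false and true, and a brochure effect would be understated.

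**Working it through.** **1. The plan's own figure.** Inputs are from the SAP (Statistical Power): 1,990 + 894 + 758 = 3,642 mailed; 20% attrition; ICC 0.05; 20 patients per provider; 4.21% v 6.55%; two-sided α = 0.05. The allocation ratio is not stated, so 1:1 is assumed.

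- Design effect = 1 + 19 × 0.05 = 1.95.
- Effective n per group = 3,642 × 0.8 / 1.95 = 1,494.
- Power (pooled two-proportion test) = 80.95%, and the smallest detectable rate is 6.52%. The stated 80% and 6.55% are reproduced.
- Target difference = 6.55 − 4.21 = 2.34 points.

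**2. Effect of the exclusion.** Let p0 = 4.21% be the control event rate before removal, including leavers; L the share who leave VA care within six months of index; and f the share of non-event controls removed because they were later mailed. L and f are assumptions.

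- Remaining fraction of controls: D = p0 + (1 − p0)(1 − f)
- Control rate = p0 / D; leaver share = L / D; genuine-event share = (p0 − L) / D

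With L = 1% and the intervention rate held at 6.55%:

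| f | D | Control rate | Rise (points) | of which leavers | of which genuine | Difference left | Power |
|---|---|---|---|---|---|---|---|
| 0 | 1.000 | 4.21% | 0 | 0 | 0 | 2.34 | 81% |
| 10% | 0.904 | 4.66% | 0.45 | 0.11 | 0.34 | 1.89 | 61.5% |
| 20% | 0.808 | 5.21% | 1.00 | 0.24 | 0.76 | 1.34 | 34% |
| 30% | 0.713 | 5.91% | 1.70 | 0.40 | 1.29 | 0.64 | 11% |
| 40% | 0.617 | 6.83% | 2.62 | 0.62 | 1.99 | −0.28 | n/a |
| 50% | 0.521 | 8.08% | 3.87 | 0.92 | 2.95 | −1.53 | n/a |

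Parts may differ from totals in the last digit through rounding. Power keeps 1,494 per group and so ignores the smaller control group.

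**3. Range for the leaver part alone.**

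- L = 0.5%, f = 25%: 0.005 / 0.7605 = 0.66% of controls v 0.5% of intervention patients.
- L = 1%, f = 50%: 0.01 / 0.521 = 1.92% v 1.0%.
- L = 2%, f = 50%: 0.02 / 0.521 = 3.84% v 2.0%.
- At f = 10%, with L from 0.5% to 2%, the gap is only 0.05 to 0.21 points.

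**4. Would removing leavers be enough?** At L = 1%, f = 50%, taking out every leaver leaves (0.0421 − 0.01) / (0.52105 − 0.01) = 6.28%. Without the exclusion the same group would show 0.0321 / 0.99 = 3.24%. About 3 points of inflation remain.

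**5. The opposing route.** Suppose non-attenders are analysed and leave at three times the attenders' 1% (assumption). Intervention leavers are then 0.8 × 1% + 0.2 × 3% = 1.4%. The control share exceeds this only if 1 / D > 1.4, that is, f above about 30%. At twice the rate the threshold is about 17%, and at five times about 46%.

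**6. Leavers without any exclusion.** If 4.21% and 6.55% are true stopping rates and 2% of the others leave in both groups, the observed rates are 4.21 + 0.9579 × 2 = 6.13% and 6.55 + 0.9345 × 2 = 8.42%. The difference is 2.29 points and power falls to 67.5%.

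**The case against.** A reader might infer that misclassification is in fact larger in the historical group. The documents do not support that. It needs equal leaving rates, and the entry rules differ: controls were seen, while intervention patients were mailed, with 20% non-attendance assumed. If non-attenders leave more often, step 5 shows that the leaver imbalance can vanish or reverse. This objection stands against any net claim about leavers. It does not touch the over-representation of genuine stoppers.

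A reader might also take leavers for the main problem. At L = 1%, f = 50% they account for 0.92 of a 3.87-point rise. The rest comes from selecting controls on the future.

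The overlap may be small. Re-entry requires eligibility to be met again and an appointment while the provider is assigned to that drug group. Events can be removed too: a patient on a reduced PPI dose still qualifies, because the PPI group admits any dose. The rise in the total rate would then be less than tabulated. Both points are fair, and are why no single figure can be given.

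The SAP regards a 15% intervention rate as reasonable to expect. Against 15 − 4.21 = 10.79 points, a shift of 0.45 to 3.87 would shrink the estimate rather than hide it.

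Finally, requiring later VA contact may discard real successes, such as a patient who stops their only VA drug and has no visit for six months. Death is not comparable in this respect. The activity restriction therefore belongs in a sensitivity analysis.

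The SAP's control-site trend analysis (Other analytical subsets) gives no reassurance. Nobody there is mailed, so the exclusion removes nobody, and a flat trend is compatible with any size of this bias.

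**Conclusion.** Two gaps stand on the text alone. Neither document has a rule for living patients who leave VA care, and the historical controls are filtered on retention and drug use after their outcome window has closed. Other things equal, the filter raises the control rate and works against the brochure.

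The size is unknown. If 10% to 50% of non-event controls are removed and no events are, 4.21% becomes about 4.7% to 8.1%. Leavers contribute about 0.1 to 0.9 points of that if 1% leave. At 40% removal or more, the whole 2.34-point detectable difference would be absorbed.

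The documents do not establish that the net misclassification is greater in controls, that a real effect was hidden, or that dealing with leavers would repair the comparison.

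**What to change.** 1. Report, by cohort, how many patients had no VA dispensing and no VA encounter in the six months after index. Add a sensitivity analysis, applied identically to both cohorts, in which their non-refill is not counted as cessation. State that this conditions on contact after index and may drop some true stoppers.
2. Report how many historical controls were removed because they later entered an intervention cohort. Add an analysis that keeps them as controls, with a patient-level correlation term for people who appear in both periods.
3. Define entry by the same visit-based rule in both cohorts, and state it in both documents.

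The cost is one activity flag and one overlap count from CDW, two further model fits, and a few lines of SAP text. No new data collection is needed. Item 1 alone would leave the larger component in place, so items 1 and 2 belong together.
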